#### 1.3. STUDY RATIONALE

As noted above, oritavancin is a weak inhibitor of CYP2C9 based on a 31% increase (90% confidence interval (CI) [1.294, 1.345]) in the systemic exposure of S warfarin (TMC-ORI-12-03). Two additional studies are ongoing; MDCO-ORI-14-01 is a Phase I study in healthy volunteers to assess the magnitude and duration of the effect of a single 1200 mg intravenous dose on numerous coagulation tests, including PT/INR, and MDCO-ORI-14-02 which is an additional Phase I study in healthy volunteers assessing the magnitude and duration of the pharmacokinetic (PK) interaction between warfarin and oritavancin. Since warfarin is a drug with a narrow therapeutic index and some patients with ABSSSI may receive oritavancin while on warfarin treatment, this study is being conducted to characterize the effect of oritavancin on clinical care and warfarin dosing. The intention is to determine the magnitude and duration, if any, of alterations to warfarin dosing or of clinically important consequences of dosing with oritavancin.

In the SOLO and SIMPLIFI trials, a total of 16 patients with ABSSSI received concomitant warfarin while treated with a single 1200 mg dose of oritavancin. Of these 16 patients, 10 were on warfarin prior to starting oritavancin, 4 received warfarin therapy after starting oritavancin therapy and for 2 patients the timing of warfarin therapy is unknown. None of these 16 patients discontinued from the study early due to adverse events. One patient experienced an event of infusion site thrombosis 2 days prior to the administration of warfarin therapy but there were no other bleeding or thrombotic related events. Additionally, no abnormal prothrombin time coagulation tests were reported in the oritavancin treated patients.

This study will extend the above safety data in patients with ABSSSI when oritavancin and warfarin are given concomitantly.

In addition, a group of patients with ABSSSI, who are not on concomitant warfarin therapy, have been added to this study to obtain information regarding the potential for antibody production following a single dose of oritavancin administration in patients. This has not been previously tested, therefore plasma will be collected at regular intervals after oritavancin dosing to test for immunoglobulins, direct and indirect Coombs, and presence of oritavancin antibodies.

The 1200 mg dose of oritavancin is the United States (US) approved therapeutic dose.

This study will also be conducted in compliance with Good Clinical Practices (GCP) including the Declaration of Helsinki and all applicable regulatory requirements.

#### 1.4. STUDY POPULATION

Subjects at least 18 years of age with an ABSSSI, on concomitant warfarin therapy, suspected or confirmed to be caused by Gram-positive pathogens. An ABSSSI includes the following infections: Wound infections, cellulitis/erysipelas and major cutaneous abscess. An additional group of patients with ABSSSI, who are not on concomitant warfarin therapy, will also be enrolled.

#### 2. TRIAL OBJECTIVE AND PURPOSE

The primary objectives of this study are:

- To assess the safety and tolerability when a single 1200 mg IV infusion of oritavancin is given concomitantly in subjects on chronic warfarin therapy with ABSSSI.
- An additional group of patients with ABSSSI, who are not on concomitant warfarin therapy, will be enrolled to obtain information regarding the potential for antibody production following a single dose of oritavancin administration in patients.

#### 3. TRIAL DESIGN

#### 3.1. PRIMARY OUTCOME

The primary outcome of this trial will be:

 Safety of the administration of oritavancin in subjects on chronic warfarin will be assessed according to vital signs, laboratory abnormalities, and the incidence of AEs and SAEs.

# 3.2. SECONDARY OUTCOME

The secondary outcome of this trial will be:

 Clinical cure determined by the Investigator at 48-72 hours after start of oritavancin dose and Day 7 visit.

#### 3.2.1. Exploratory Outcome:

• An exploratory outcome of this trial is to evaluate the potential for antibody development following a single dose oritavancin administration.

## 3.3. MEASURES TO MINIMIZE/AVOID BIAS

# 3.3.1. Unblinded Study

This is an open label study. The primary endpoints are safety and laboratory measurements, primarily change in PT/INR, which is not likely to be subject to interpretation bias.

#### 3.4. TYPE/DESIGN OF TRIAL

This will be a Phase IV, open-label study evaluating the safety and tolerability when a single 1200 mg dose of oritavancin is given concomitantly in subjects on chronic warfarin therapy with ABSSSI. An additional group of patients with ABSSSI, who are not on concomitant warfarin therapy, will also be enrolled.

Up to 40 subjects will be enrolled at up to 10 centers in the United States. Informed consent will be obtained from subjects meeting all inclusion and no exclusion criteria before the initiation of any study-specific procedures.

Eligible subjects will be enrolled and receive a single 1200 mg dose of oritavancin IV.

Adverse events and SAEs will be assessed from the time of informed consent through 14 days post administration of oritavancin.

A description of each study period and the assessments that will be performed at each time point is detailed in Section 6.

#### 4. SUBJECT POPULATION

#### 4.1. NUMBER OF SUBJECTS

Up to forty subjects will be enrolled at up to 10 centers in the US. Approximately 25 subjects on concomitant warfarin therapy will be enrolled in this study. An additional 15 patients with ABSSSI, who are not on warfarin, will also be enrolled.

## 4.2. INCLUSION CRITERIA

Subjects may be included in the study if they meet all of the following criteria:

- 1. Males or females ≥18 years old
- 2. Diagnosis of ABSSSI (wound infections, Cellulitis/erysipelas, or cutaneous abscess) suspected or confirmed to be caused by a Gram-positive pathogen requiring IV therapy
- 3. Must be currently being treated with chronic warfarin therapy\*:
  - a. Warfarin therapy must have been initiated a minimum of 30 days prior to enrollment
  - b. Current warfarin dosage must be stable for at least 14 days prior to enrollment
  - c. At least one documented INR between 1.5 and 3.0 in the 30 days prior to Screening
  - d. The INR value at Screening must fall within 1.5 and 3.0 and also be within 25% of the prior documented value
- 4. Able to give informed consent and willing to comply with all required study procedures
- \*Patients in the non-warfarin sub-group are not required to be on chronic warfarin therapy

#### 4.3. EXCLUSION CRITERIA

Subjects will be excluded from the study if any of the following exclusion criteria apply:

- 1. Infections associated with, or in close proximity to, a prosthetic device
- 2. Severe sepsis or refractory shock
- 3. Known or suspected bacteremia at time of screening
- 4. ABSSSI due to or associated with any of the following:
  - a. Infections suspected or documented to be caused by Gram-negative pathogens (i.e., human or animal bites, injuries contaminated with fresh or salt water, external malignant otitis)
  - b. Wound infections (surgical or traumatic) and abscesses with only Gramnegative pathogens

- c. Diabetic foot infections (infection extending distal to the malleoli in a patient with diabetes mellitus and peripheral neuropathy and/or vascular insufficiency or any ulceration of their foot)
- d. Concomitant infection at another site not including a secondary ABSSSI lesion (e.g., septic arthritis, endocarditis, osteomyelitis)
- e Infected burns
- f. A primary infection secondary to a pre-existing skin disease with associated inflammatory changes such as atopic dermatitis, eczema or hidradenitis suppurativa
- g. Decubitus or chronic skin ulcer, or ischemic ulcer due to peripheral vascular disease (arterial or venous)
- h. Any evolving necrotizing process (i.e. necrotizing fasciitis), gangrene or infection suspected or proven to be caused by Clostridium species (e.g., crepitance on examination of the ABSSSI site and/or surrounding tissue(s) or radiographic evidence of subcutaneous gas in proximity to the infection)
- i. Infections known to be caused by a Gram-positive organism with a vancomycin minimum inhibitory concentration (MIC) >2  $\mu$ g/mL or clinically failing prior therapy with glycopeptides
- i. Catheter site infections
- 5. Currently receiving chronic systemic immunosuppressive therapy such as chemotherapy or prednisone (prednisone at non-immunosuppressive doses of ≤15 mg/day is permitted)
- 6. Subjects who are likely to need treatment with intravenous unfractionated heparin sodium within 48 hours after oritavancin administration
- 7. Last known cluster of differentiation 4 (CD4) count <200 cells/mm3 in subjects with known human immunodeficiency virus (HIV)/acquired immune deficiency syndrome (AIDS)
- 8. Neutropenia with absolute neutrophil count (ANC) <500 cells/mm3
- 9. Significant or life-threatening condition (e.g., endocarditis) that would confound or interfere with the assessment of safety
- 10. Women who are pregnant or nursing, or who are of childbearing potential and unwilling to use at least 2 acceptable methods of birth control: (e.g., prescription oral contraceptives, contraceptive injections, contraceptive patch, intrauterine device, barrier method(s) or male partner sterilization). Women ≥2 years postmenopausal or surgically sterile are exempt from this exclusion
- 11. History of immune-related hypersensitivity reaction to glycopeptides (such as vancomycin, televancin, daptomycin, or dalbavancin) or any of their excipients.

  Note: subjects who have had histamine-like infusion reactions to a glycopeptide are not excluded
- 12. Subjects unwilling to forego blood and/or blood product donation for at least 1 month from initiation of oritavancin dose

- 13. Treatment with investigational medicinal product within 30 days or 5 half-lives, whichever is longer, before enrollment and for the duration of the study
- 14. Investigational device present, or removed within 30 days before enrollment, or presence of device-related infection
- 15. Significant change of any medications over the preceding 7 days that could interfere with the metabolism of warfarin (if patient is on chronic warfarin therapy)
- 16. Subjects who the investigator considers unlikely to adhere to the protocol, comply with oritavancin administration, or complete the clinical study (e.g., unlikely to survive 90 days from initiation of oritavancin dosing)

Subjects excluded for any of the previous criteria may only be rescreened for participation after favorable discussion with sponsor and principal investigator

#### 4.4. WITHDRAWAL CRITERIA

All subjects have the right to withdraw at any point during the study without prejudice. The investigator can discontinue any subject at any time if medically necessary. It will be documented whether or not each subject completes the clinical study. If for any reason study treatment or observations are discontinued, the reason will be recorded and the Sponsor should be notified. Reasons that a subject may discontinue participation in this clinical study include the following:

- Adverse event(s)
- Death
- Withdrawal of consent by subject
- Physician decision
- Lost to follow-up

It is imperative to obtain safety follow-up information for all subjects whether or not they discontinue oritavancin. Every attempt should be made to collect follow-up information except for those subjects who specifically withdraw consent for release of such information.

#### 5. TREATMENT OF SUBJECTS

# 5.1. STUDY MEDICATIONS

Each subject will receive a single 1200 mg IV dose of oritavancin. Oritavancin will be prepared by the study pharmacist/designee.

#### 5.1.1. Oritavancin

Oritavancin will be supplied as a lyophilized powder in single-use glass vials. Each vial will contain 400 mg of oritavancin.

Three 400-mg vials will be required for each subject receiving oritavancin. At the time of use, each vial will be reconstituted by adding 40 mL of Sterile Water for Injection, United States Pharmacopeia, to each 400-mg vial of oritavancin. Vials reconstituted in this manner will provide a 10 mg/mL solution. After reconstitution, oritavancin should be further diluted in 5% dextrose in water (D5W) to provide a total volume of approximately 1000 mL. Since the solubility of oritavancin is highly dependent upon pH, no other material or diluent may be substituted or concomitantly infused through the same IV line. The IV line should be flushed with D5W before and after; saline must not be used since it may cause precipitation.

Each subject will receive a single oritavancin dose of 1200 mg in 1000 mL of D5W administered as a constant-rate IV infusion over 3 hours via a single dedicated peripheral IV line. Oritavancin must be infused over 3 hours (6.7 mg/minute) to reduce the potential for histamine-like infusion reactions or phlebitis.

### 5.1.2. Packaging and Labeling

Oritavancin will be provided by the Sponsor. Warfarin will be supplied by the site. Infusion bags of D5W will be provided by the study site pharmacy.

Medication labels will comply with regulatory requirements. The storage conditions for each medication provided will be described on the medication label.

# **5.1.3. Storage**

Oritavancin lyophilized powder should be stored in a secure cabinet or other enclosure at controlled room temperature (20°C to 25°C; 68°F to 77°F). Diluted intravenous solution in an infusion bag should be used within 6 hours when stored at room temperature, or used within 12 hours when refrigerated at 2 to 8°C (36 to 46°F). The combined storage time (reconstituted solution in the vial and diluted solution in the bag) and 3 hour infusion time should not exceed 6

hours at room temperature or 12 hours if refrigerated (see Pharmacy Manual). Access should be strictly limited to the study pharmacists and their designees.

# 5.1.4. Accountability

The investigator or designee must maintain an inventory record of all study medications received and administered to assure the regulatory authorities and the Sponsor that the drug will not be dispensed to any person who is not a subject under the terms and conditions set forth in this protocol. Drug accountability forms and/or specific instructions can be found in the Pharmacy Manual.

The oritavancin supplied for use in this study is to be prescribed only by the principal investigator or designated sub-investigators and may not be used for any purpose other than that outlined in this protocol.

During the study, all used oritavancin containers (e.g., empty vials/bottles) will be kept until the monitor has reviewed the accountability records.

All used and unused oritavancin supplied for this study will be destroyed on site once inventoried and the monitor has reviewed the accountability records. In the event that oritavancin needs to be returned for any other reason, the site will receive a written request listing the drug lot number(s) to be returned and the reason for the return request.

## 5.2. CONCOMITANT MEDICATIONS

#### **5.2.1.** Prohibited Concomitant Medications

If possible, patients on chronic warfarin therapy should not take any new medications that could interfere with warfarin metabolism, other than oritavancin, during this study. Any concomitant medications will be recorded in the electronic case report form (eCRF) according to the Schedule of Events.

#### **5.2.2.** Permitted Concomitant Medications

Subjects enrolled and treated with oritavancin may receive additional antibiotic therapy with gram-negative coverage if necessary.

## **5.2.3.** Warfarin Therapy

Any changes in warfarin dosing (for patients on concomitant chronic warfarin), based on the PT/INR results or safety data will be captured.

#### 5.3. RESTRICTIONS

Subjects will be encouraged to continue their usual diet and level of activity, as dictated by their clinical condition. Activities that would impact clinical outcome should be avoided during the study period.

# 6. SEQUENCE OF PROCEDURES

A summary of clinical assessments and procedures is provided before the contents in Schedule of Events.

This study consists of four periods: Screening, Pre-Dose, Treatment, and Follow-up. The maximum duration of a patient's participation in this study is approximately 14 days post first administration of oritavancin.

#### 6.1. GENERAL CONDUCT OF THE TRIAL

Written informed consent will be obtained from all subjects by the site staff member before any study-specific procedure is performed.

# **6.2.** SCREENING PERIOD (≤24 HRS PRIOR TO DAY 1)

The following procedures will be performed  $\leq$  24 hours prior to Day 1 to establish each candidate's general health and qualifications for enrollment into the study:

- Obtain written informed consent
- Verify inclusion/exclusion criteria
- Record medical history and demographics
- Obtain height and weight to determine body mass index (BMI)
- Perform a physical examination
- Obtain vital sign measurements (blood pressure, heart rate, respiratory rate and temperature)
- Collect blood specimens for hematology, serum chemistry, immunoglobulin panel, oritavancin antibody assay, PT/INR coagulation test, direct and indirect Coombs test
- A urine pregnancy test will be performed for female subjects of childbearing potential. This test may be omitted for females >2 years postmenopausal or surgically sterile.
- Microbiology samples, if obtained, per standard of care
- Record medication history over the past 14 days, including over-the-counter (OTC), prescription drugs, vitamins and nutraceuticals (e.g., herbal supplements)

- Assessment of AEs and SAEs starting from the time the informed consent form is signed
- Record planned ABSSI surgical procedures

#### 6.3. DAY 1 PRE-DOSE

The following pre-dose procedures will be performed at Day 1 prior to administration of oritavancin:

- Vital signs (blood pressure, heart rate, respiratory rate and temperature)
- Confirm that the subject continues to meet inclusion and exclusion criteria including the verification of safety lab results
- Collection of concomitant medication information
- Assessment of AEs and SAEs

#### 6.4. TREATMENT PERIOD

The enrollment process will be initiated only after confirmation of a subject's eligibility. Each successive subject will be assigned a unique subject identification number.

If a subject is found to be ineligible after signing the informed consent, but prior to dosing, he or she will be considered a screen failure, the subject will not be enrolled, and oritavancin will not be administered.

## 6.4.1. Day 1

Ideally, treatment should be initiated within 4 to 6 hours after the patient is first seen on Day 1.

- Administer oritavancin as a single IV infusion of 1200 mg over 3 hours
- Vital signs (blood pressure, heart rate, respiratory rate and temperature)
- Collection of concomitant medication information.
- Assessment of AEs and SAEs
- Collect blood sample for Drug Dependent Antibody Ex Vivo Study (immediately after the completion of the oritavancin infusion).

## 6.5. FOLLOW UP

#### 6.5.1. Day 2

 Collect blood sample for PT/INR coagulation test (window: 18-36 hours after the start of the oritavancin infusion).

## 6.5.2. Day 3

- Vital signs (blood pressure, heart rate, respiratory rate and temperature)
- Assessment of early clinical cure at 48-72 hours after start of infusion of Oritavancin
- Assessment of AEs and SAEs
- Collect blood specimens for immunoglobulin panel, oritavancin antibody assay, PT/INR coagulation test, direct and indirect Coombs test
- Collection of concomitant medication information

# 6.5.3. Day 7

- Obtain vital sign measurements (blood pressure, heart rate, respiratory rate and temperature)
- Collect blood specimens for hematology, serum chemistry, immunoglobulin panel, oritavancin antibody assay, PT/INR coagulation test, direct and indirect Coombs test
- A urine pregnancy test will be performed for female subjects of childbearing potential. This test may be omitted for females >2 years postmenopausal or surgically sterile.
- Assessment of clinical cure
- Collection of concomitant medication information
- Assessment of AEs and SAEs

#### 6.5.4. Day 14 ( $\pm 2$ days)

- Vital signs (blood pressure, heart rate, respiratory rate and temperature)
- Collection of concomitant medication information
- Collect blood specimens for hematology, serum chemistry, immunoglobulin panel, oritavancin antibody assay, PT/INR coagulation test\*, direct and indirect Coombs test
- Assessment of AEs and SAEs
- Patients with a negative Coombs Test at Day 14 test must have test repeated every 2 weeks until return to baseline or stable.

\*If a subject's PT/INR has not returned to therapeutic baseline by Day 14, patient will be referred to and followed by their primary physician responsible for their PT/INR monitoring.

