**Table 1: SCHEDULE OF EVENTS** 

Study procedures	SCREENING	Pre-Dose	Treatment	FOLLOW UP			
	≤24 hrs from 1 st dose	Day 1	Day 1	Day 2	Day 3 Safety & Efficacy Visit	Day 7 Safety & Efficacy Visit	Day 14 Follow up Visit (± 2 days) 
Informed Consent	X						
Assess Inclusion/Exclusion	X	X					
Medical History	Х						
Physical Exam (height and weight at Screening only)	х						
Vital Signs 	X	X	X		X	X	X
Pregnancy test 	X					X	
Record ABSSSI surgical procedures 	X						
Safety laboratory assessments 	Х					X	X
Microbiology testing 	X						
Record prior or concomitant medications	X	X	X	X	X	X	X
Administer IV oritavancin			X				
PT/INR Test 	X			X	X	X	X
Assess clinical cure 					X	X	
Immunoglobulin panel and plasma for oritavancin antibody assay	Х				Х	х	х
Direct and Indirect Coombs Test 	Х				Х	х	Х
Assessment of adverse events 	Х	X	X	Х	X	X	X
Plasma Storage Samples for Drug Dependent Antibody Ex Vivo Study 			Х				

<sup>1 If subject has abnormal laboratory values that have not returned to a therapeutic baseline by Day 14, additional follow up visits may be required.

<sup>2 Vitals signs include blood pressure, temperature, respiratory rate and heart rate.

<sup>3 Perform a local urine pregnancy test for female patients of childbearing potential (may be omitted for females > 2 years postmenopausal or surgically sterile).

<sup>4 This includes but is not limited to aspiration, debridement, incision and drainage.

<sup>5 Blood chemistry and hematology (Section 7.2.4 for listing of tests to be performed). Unless otherwise indicated all laboratory tests will be performed by site's local laboratory.

<sup>6 Microbiology testing should be performed per institutions Standard of Care (SOC).

<sup>7 Patients on warfarin are required to have at least one documented INR between 1.5 and 3.0 in the 30 days prior to screening. The INR value at Screening must fall within 1.5 and 3.0. After dosing with oritavancin, the next PT/INR should be collected with 18-36 hours of start of oritavancin infusion. If PT/INR has not returned to baseline at Day 3, more frequent PT/INR testing prior to Day 7 may be required.

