## 7.2.4. Laboratory assessment

Specimens will be obtained at the designated time periods as indicated in the Schedule of Events. All clinical laboratory assessments will be performed by the site's local laboratory. Additional local laboratory testing may be performed at the discretion of the investigator. Any clinically significant lab findings that occur during the study should be followed to resolution per the Investigator/Sponsor's decision. If the PT/INR has not returned to baseline by Day 14, patient will be followed until PT/INR has returned to therapeutic baseline.

- Chemistry: Blood urea nitrogen, Serum creatinine, Total bilirubin, Direct bilirubin, Alkaline phosphatase, Aspartate aminotransferase, Alanine aminotransferase, Albumin, Total protein, Glucose, Calcium, Chloride, Sodium, Magnesium, Potassium, Uric acid, Lactate dehydrogenase, Bicarbonate, Phosphorus
- **Hematology:** Hemoglobin, Hematocrit, White blood cell count (with automated differential), Red blood cell count, Platelet count
- Coagulation Tests: PT/INR
- Urine Pregnancy Test
- Direct and Indirect Coombs test
- Immunoglobulin Panel Assays: Immunoglobulin M (IgM), Immunoglobulin G (IgG); Immunoglobulin E (IgE), Immunoglobulin A (IgA),
- Assay for oritavancin antibodies
- Plasma Storage Samples for Drug Dependent Antibody Ex Vivo Study

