#### 8. ADVERSE EVENTS

# 8.1. **DEFINITIONS**

#### 8.1.1. Adverse Event

An adverse event (AE) is defined as any untoward medical occurrence in a subject or clinical investigation subject administered a medicinal product and which does not necessarily have a causal relationship with this treatment. An AE can therefore be any unfavorable and unintended sign (including an abnormal laboratory finding), symptom or disease temporally associated with the use of a medicinal product, whether or not considered related to the medicinal product.

Planned hospital admissions and/or surgical operations for an illness or disease that existed before the drug was given or the subject was enrolled in a clinical study are not to be considered AEs.

Subjects experiencing adverse events should be followed clinically until their health has returned to baseline status or until all parameters have returned to normal or have otherwise been explained. It is expected that the investigator will provide or arrange appropriate supportive care for the subject if necessary.

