3.3 Study Design

This will be a Phase IV, open-label study evaluating the safety and tolerability when a single 1200 mg dose of oritavancin is given concomitantly in subjects on chronic warfarin therapy with ABSSSI. An additional group of patients with ABSSSI, who are not on concomitant warfarin therapy, will also be enrolled.

Up to 40 subjects will be enrolled at up to 10 centers in the United States. Informed consent will be obtained from subjects meeting all inclusion and no exclusion criteria before the initiation of any study-specific procedures.

Eligible subjects will be enrolled and receive a single 1200 mg dose of oritavancin IV.

Adverse events and SAEs will be assessed from the time of informed consent through 14 days post administration of oritavancin.

The schedule of events is shown in [Table 1](#). This schedule is based on Protocol MDCO-ORI-14-03, Amendment 2 (17 March 2016). In Protocol Amendment 1 (dated 16 December 2015), Direct Coombs Test (DAT) was added to the schedule of events; in Protocol Amendment 2, Indirect Coombs Test (IAT) and the drug dependent antibody was added to the schedule of events.

Table 1: Schedule of Events

Study procedures	SCREENING ≤24 hrs from 1st dose	Pre-Dose	Treatment	FOLLOW UP			
				Day 1	Day 2	Day 3 Safety & Efficacy Visit	Day 7 Safety & Efficacy Visit
Informed Consent	x						
Assess Inclusion/Exclusion	x	x					
Medical History	x						
Physical Exam (height and weight at Screening only)	x						
Vital Signs ²	x	x	x		x	x	x
Pregnancy test ³	x					x	
Record ABSSI surgical procedures ⁴	x						
Safety laboratory assessments ⁵	x					x	x
Microbiology testing ⁶	x						
Record prior or concomitant medications	x	x	x	x	x	x	x
Administer IV oritavancin			x				
PT/INR Test ⁷	x			x	x	x	x
Assess clinical cure ⁸					x	x	
Immunoglobulin panel and plasma for oritavancin antibody assay	x				x	x	x
Direct and Indirect Coombs Test ⁹	x				x	x	x
Assessment of adverse events ¹⁰	x	x	x	x	x	x	x
Plasma Storage Samples for Drug Dependent Antibody Ex Vivo Study ¹¹			x				

¹ If subject has abnormal laboratory values that have not returned to a therapeutic baseline by Day 14, additional follow up visits may be required.

² Vitals signs include blood pressure, temperature, respiratory rate and heart rate.

³ Perform a local urine pregnancy test for female patients of childbearing potential (may be omitted for females > 2 years postmenopausal or surgically sterile).

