8.2 Clinical Laboratory Assessments

Clinical safety laboratory values and changes from baseline of hematology, serum chemistry, and urinalysis, including prothrombin time (PT)/international normalized ratio (INR), direct and indirect Coombs (DAT and IAT), Immunoglobulin panel, oritavancin antibody assay, will be summarized descriptively. Potentially clinically significant (PCS) values will also be flagged in a listing. The criteria for potentially clinical significant liver function tests are displayed in [Table 2](#).

Unscheduled assessments that are not used for baseline will not be included in summary tables; however, all measurements will be listed.

Table 2: Criteria for Potential Clinically Significant Abnormal Lab Tests

Parameter	Lower limit	Upper limit
Hematology		
Red Blood Cell Count	$\leq 0.75 \times \text{LLN}$	$\geq 1.25 \times \text{ULN}$
WBC's Count	$< 2.0 \times 10^9/\text{L}$	
Hematocrit	$\leq 0.75 \times \text{LLN}$	$\geq 1.25 \times \text{ULN}$
Hemoglobin	$\leq 11.5 \text{ g/dL}$ Male	$\geq 18.0 \text{ g/dL}$ Male
	$\leq 9.5 \text{ g/dL}$ Female	$\geq 16.0 \text{ g/dL}$ Female
Platelet count	$\leq 75 \times 10^9/\text{L}$	$\geq 700 \times 10^9/\text{L}$
Serum Chemistry		
BUN		$\geq 10.7 \text{ mmol/L}$
Calcium	$\leq 7.0 \text{ mg/dL}$	$\geq 15.5 \text{ mg/dL}$
Creatinine		$\geq 2.0 \text{ mg/dL}$
Glucose	$\leq 50 \text{ mg/dL}$	$\geq 180 \text{ mg/dL}$
Potassium	$\leq 3.0 \text{ mmol/L}$	$\geq 5.5 \text{ mmol/L}$
Sodium	$\leq 125 \text{ mmol/L}$	$\geq 150 \text{ mmol/L}$
Liver Function Tests (LFTs)		
Alanine Transaminase (ALT/SGPT) $\geq 3x, 5x, 10x$ and $20x \text{ ULN}$		
Aspartate Transaminase (AST/SGOT) $\geq 3x, 5x, 10x$ and $20x \text{ ULN}$		
ALT or AST $\geq 3x, 5x, 10x$, or $20x \text{ ULN}$		
Total bilirubin $\geq 1.5x$ and $2x \text{ ULN}$		
Alkaline Phosphatase (ALP) $\geq 1.5x$ and $3x \text{ ULN}$		
ALT/AST $\geq 3x \text{ ULN}$ and Total bilirubin $\geq 2x \text{ ULN}$;		
Potential Hy's Law cases: ALT or AST $\geq 3 \times \text{ULN}$, Total bilirubin $\geq 2 \times \text{ULN}$, and ALP $\leq 2 \times \text{ULN}$		

LLN: lower limit of the standard reference (normal) range.

ULN: upper limit of the standard reference (normal) range.

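### The Day 14 Coombs rule makes a negative result the trigger for mandatory repeats, probably a slip for positive, so a subject positive on both tests has no mandatory repeat

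*Protocol*

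**What the plan says.** Direct and indirect Coombs tests are scheduled at Screening, Day 3, Day 7 and Day 14. For what happens after that, Protocol 6.5.4 says: "Patients with a negative Coombs Test at Day 14 test must have test repeated every 2 weeks until return to baseline or stable". Footnote 9 to Table 1 repeats the sentence in the protocol and again in the SAP.

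Three general clauses could also reach an abnormal Coombs result at Day 14:

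- Protocol Table 1, footnote 1: "If subject has abnormal laboratory values that have not returned to a therapeutic baseline by Day 14, additional follow up visits may be required".
- Protocol 7.2.4: "Any clinically significant lab findings that occur during the study should be followed to resolution per the Investigator/Sponsor's decision".
- Protocol 8.1.1, which allows an abnormal laboratory finding to count as an adverse event and adds: "Subjects experiencing adverse events should be followed clinically until their health has returned to baseline status".

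Protocol Section 6 sets the expected length of participation: "The maximum duration of a patient's participation in this study is approximately 14 days post first administration of oritavancin". On the analysis side, SAP 8.2 summarises both Coombs tests descriptively and adds: "Unscheduled assessments that are not used for baseline will not be included in summary tables; however, all measurements will be listed".

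**The concern.** Protocol 1.3 explains that Coombs tests are among the assays used to look for antibody production after oritavancin, a question it describes as not previously tested. A positive result is therefore the finding of interest, and a positive result still present at the last scheduled visit is the one that needs following. The only mandatory rule for Coombs testing beyond Day 14 instead names the subjects whose result is negative.

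A site that applies the rule as written would repeat tests in subjects with nothing to follow, and would leave those still positive to the investigator's judgement. A site that silently reads *positive* for *negative* departs from the approved text. With up to 10 centres, practice could differ between them.

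**Working it through.** No arithmetic applies. The check is whether the rule makes sense as worded, whether it is stated correctly anywhere, and whether another clause closes the gap.

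**1. Is it stated correctly anywhere?** No. Protocol 6.5.4, Protocol Table 1 footnote 9 and SAP Table 1 footnote 9 all use *negative*. This is current text in both documents, not a record of superseded wording.

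**2. Does the trigger fit the stopping rule?** Take a negative Day 14 result against each possible baseline.

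- Baseline negative: the subject is already at baseline, so the stopping condition is met before the first repeat.
- Baseline positive: returning to baseline would mean waiting for the test to turn positive again.
- No baseline result: there is nothing to return to.

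Now take a subject negative at baseline and positive at Day 14. Here the stopping rule has a natural meaning, and the literal rule leaves this subject out. The neighbouring PT/INR note in 6.5.4 is built the sensible way: it acts on results that have not come back to baseline by Day 14.

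**3. Whom does the literal rule miss?** Two tests are done, but the rule speaks of a single Coombs test.

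- Positive on both at Day 14: not covered, so no mandatory repeat.
- Positive on one and negative on the other: the subject does have a negative test, so the rule can be read to apply, but it does not say which test to repeat.
- Positive at Day 3 or Day 7 and negative on both by Day 14: covered by the literal wording.

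**4. Do the general clauses close the gap?** Not fully.

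- Table 1 footnote 1 only permits extra visits.
- Section 7.2.4 depends on the result being judged clinically significant and on the investigator's or sponsor's decision. SAP Table 2, which sets thresholds for potentially clinically significant laboratory values, has no Coombs entry.
- Section 8.1.1 applies only if the result is treated as an adverse event. Section 8.2 ends the recording of non-serious events 14 days after dosing, while the Day 14 visit may be as late as Day 16, which is 16 − 1 = 15 days after dosing on Day 1.

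None of the three names the Coombs test or sets an interval.

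**5. Does any analysis change?** No. The scheduled Coombs results are collected and summarised whatever the footnote says. Repeats after Day 14 have no visit in the schedule, so under SAP 8.2 they would be listed and not summarised.

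**The case against.** The strongest reply is that this is a wording error that any investigator would see through. The intended meaning can be recovered from the sentence itself. A positive subject is not abandoned, because clinically significant findings should be followed to resolution, extra visits are allowed, and an adverse event is followed to baseline or normal. No endpoint moves.

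Much of that stands, and it limits the point. A reader might infer more than the documents support, in four ways:

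- *Positive subjects get no follow-up.* Not so. The general clauses allow or encourage it. What is missing is an automatic trigger and an interval.
- *Every subject positive at Day 14 lacks a mandatory repeat.* This is certain only for those positive on both tests. With discordant results the rule is ambiguous.
- *Large numbers of negative subjects will be called back.* The documents give no positivity rate. A site that treats a subject negative at both Screening and Day 14 as already back at baseline would recall none of them. No useful count can be given.
- *The antibody assessment is compromised.* Testing at Days 3, 7 and 14 is intact and the planned summaries do not use later repeats.

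What does not stand is that the clause can be left alone. It is a mandatory safety instruction, identical in three places, and relying on each site to correct it is not a substitute for correcting it.

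**Conclusion.** The rule is wrong as written and should be corrected. That *negative* is a slip for *positive* is an inference, resting on the stopping condition and on the antibody purpose of the test. The rule fails on its own terms whether or not the word was intended.

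The size is modest: a possible loss or inconsistency of safety follow-up after Day 14 in subjects positive on both Coombs tests, and uncertainty over which test to repeat in those positive on one. The ceiling is the planned enrolment of up to 40. The expected number is unknown and may be zero. The statement that no summary changes assumes that repeats after Day 14 are handled as unscheduled assessments under SAP 8.2, which is the natural reading because the schedule ends at Day 14.

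**What to change.** Replace the sentence in Protocol 6.5.4, Protocol Table 1 footnote 9 and SAP Table 1 footnote 9 with one to this effect: any subject whose direct or indirect Coombs test is positive at Day 14 must have the positive test repeated at two-week intervals until it has returned to its baseline result (or to negative, if there is no baseline result) or is stable.

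Two details matter. Naming both tests, and saying that the positive one is repeated, removes the ambiguity for discordant results. The provision for no baseline result is needed because SAP 3.3 records that the direct test joined the schedule only with Amendment 1 and the indirect test only with Amendment 2.

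Do not add a blanket exemption for subjects already positive at baseline. The stopping rule already deals with them, and an exemption would be a new clinical choice that could drop a subject whose reaction has strengthened.

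The cost is a one-sentence correction through the usual IRB/EC amendment process (Protocol 13.2), the matching edit in the SAP, and a few extra blood draws in any subject positive at Day 14. No analysis needs to change.
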